### Unscheduled Visit

An unscheduled visit may take place at any time during the study at the subject's request or as deemed necessary by the Investigator due to medical considerations. The date and reason for the unscheduled visit will be recorded. AE monitoring and concomitant medication recording will be recorded. Other procedures and evaluations will be completed as deemed necessary by the Investigator and may include (but not limited to) safety laboratory tests, ECG, vital signs and physical examination.

### Handling Subject Withdrawal

If a subject's participation in the study is prematurely terminated for any reason or fails to return for a scheduled visit, every effort should be made to determine the reason. This information will be recorded.

Upon withdrawal from the study, any time after dosing has taken place, all efforts should be made to invite the subject to complete the EOS visit.

If for any reason the subject does not agree to return to the CPU for the above visit, the reason and/or efforts made will be recorded.

If the subject withdraws from the study and also withdraws consent for disclosure of future information, no further evaluations should be performed, and no additional data should be collected. The Sponsor may retain and continue to use any data collected before such withdrawal of consent.

## 7.2. Allowed Time Window Deviations

Allowed time window deviations are (assessments at screening, Day -1, and EOS not described here):

### Vital signs

Day 1 and Day 29: predose, and 30 min ( $\pm$  5 min), 45 min ( $\pm$  5 min), 1h ( $\pm$  15 min), 3h ( $\pm$  15 min), 12h ( $\pm$  30 min), 24h ( $\pm$  1h), 48h ( $\pm$  1h) postdose.

On other dosing days, vital signs need to be assessed before dosing.

### Physical examination

Day 1 and Day 29: 6h ( $\pm$  1h), 48h ( $\pm$  2h) postdose.

On other dosing days, the physical examination needs to be performed before dosing.

### ECG

Day 1 and Day 29: predose, and 3h ( $\pm$  15 min), 6h ( $\pm$  15 min), 12h ( $\pm$  30 min), 24h ( $\pm$  1h), 48h ( $\pm$  1h) postdose.

On other dosing days, a 12-lead ECG needs to be taken before dosing.

### Audiometric testing

The allowed time window deviations for audiometric and vestibular testing during the treatment period are Screening (-42 to -8 days), Baseline (-7 to Day -1) (these two tests can be performed on the same day) Day 3 (-1 day), Day 10 (-1 day), Day 17 (-1 day), Day 24 (-1 day), and EOS (7-11 days after last dosing). The otoscopic exam on Day 3, Day 10, Day 17 and Day 24 can be performed 72 hours prior to dosing.

### Local reaction of injection

Day 1 and Day 29: 45 min ( $\pm$  5 min), 6h ( $\pm$  15 min), 12h ( $\pm$  30 min), 24h ( $\pm$  1h), 48h ( $\pm$  1h) postdose.

On other dosing days the local reaction of injection needs to be assessed up to 1h post dosing.

### For laboratory samples

#### a. Blood samples

- Safety sampling: Day 1 and Day 29: 6h ( $\pm$  15 min), 24h ( $\pm$  15 min), 48h ( $\pm$  30 min). Other safety blood samples will be taken in the morning of Day 7, Day 14, Day 21, and Day 28.
- PK sampling: Day 1 and Day 29: predose, 15 min ( $\pm$  2 min), 30 min ( $\pm$  5 min), 45 min ( $\pm$  5 min), 1h ( $\pm$  5 min), 3h ( $\pm$  15 min), 6h ( $\pm$  15 min), 12h ( $\pm$  30 min),

24h ( $\pm$  1h), 36h ( $\pm$  1h), 48h ( $\pm$  1h), 72h ( $\pm$  1h). On other dosing days, the PK blood samples will be taken predose and 1h postdose ( $\pm$  5 min).

- Housekeeping proteins: Day 1 and Day 29: predose and 24h ( $\pm$  1h), 48h ( $\pm$  1h) postdose. On other dosing days the sample needs to be taken predose.
- Blood retention sampling: Day 1 and Day 29 predose and at 3h ( $\pm$  15 min) postdose. On other dosing days the sample needs to be taken predose.

b. Urine samples

- Safety sampling: Day 1 and Day 29: 6h ( $\pm$  30 min), 24h ( $\pm$  2h), 48h ( $\pm$  2h). Other safety urine samples will be taken in the morning of Day 7, Day 14, Day 21, and Day 28.
- PK sampling: Day 1 and Day 29: predose and during 0-12h ( $\pm$  15 min), 12-24h ( $\pm$  15 min), 24-48h ( $\pm$  15 min), and 48-72h ( $\pm$  15 min) postdose. And on Day 8, 11, 15, 18, 22, and 25 for creatinine.
- Renal injury biomarkers and creatinine sampling: predose and 12h sample from last void of the 0-12h collection ( $\pm$  30 min), 24h ( $\pm$  2h), 36h ( $\pm$  2h), 48h ( $\pm$  2h), and 72h ( $\pm$  2h) postdose. And on Day 8, 11, 15, 18, 22, and 25.

### 7.3. Safety Evaluations

#### 7.3.1. Adverse Events (AEs)

Adverse events will be collected continuously starting from signing the Informed Consent Form (ICF) until EOS visit for randomized subjects.

Adverse events reported prior to dosing will be considered non treatment emergent. Any new systemic effect that occurs between scheduled visits should be brought to the attention of the Investigator and recorded in the subject's files.

Common Terminology Criteria for Adverse Events (CTCAE) will be used to determine the AE safety profile of ELX-02. For more information refer to Section 8.

#### 7.3.2. Concomitant Medications

Use and any changes in concomitant medication will be recorded continuously starting from screening until EOS visit. Contraindicated drugs are listed in Section 6.1.

#### 7.3.3. Vital Signs

Vital signs (supine BP, HR, RR, and oral temperature) will be measured in supine position after at least 5 min of supine rest at the time points specified in Section 7.1 and in Table 1.

On days when vital signs parameters need to be assessed as well as blood sampling, the vital signs will be performed before blood sampling, except when an indwelling cannula has been placed.

Changes in vital signs determined by the Investigator to be clinically significant will be noted as an AE in the eSource. Such abnormalities will be closely monitored until stabilized or resolved.

#### **7.3.4. Physical Examination**

Complete physical examination will be performed at the time-points specified in Section 7.1 and in Table 1.

Significant changes from baseline examination on screening will be recorded as AEs.

#### **7.3.5. ECG Examination**

A 12-lead ECG (taken after 5 minutes in a supine position) will be performed at the timepoints specified in Section 7.1 and in Table 1.

The following values will be collected: QT, QTc, HR, QRS, and PR.

On days when a 12-lead ECG parameters needs to be assessed as well as blood sampling, the vital signs and 12-lead ECG will be performed before blood sampling, except when an indwelling cannula has been placed.

Any ECG abnormality compared to baseline (Day 1 predose) reading determined by the Investigator to be clinically significant will be recorded as an AE. Such abnormalities will be closely monitored until stabilized or resolved.

#### **7.3.6. Auditory and Vestibular Assessments**

The following auditory and vestibular tests will take place:

- Otoscopy at all visits (the otoscopic exam on Day 3, Day 10, Day 17 and Day 24 can be performed 72 hours prior to dosing by a CPU physician)
- Tympanometry (Immittance audiometry) at all visits
- Speech Reception Threshold (SRT)- will be performed at screening and baseline. At follow up visits, SRT will be performed only if there are ASHA significant change criteria/reverse ASHA significant change criteria noted in the PTA/HFA exam.
- Pure tone audiometry (PTA) with frequencies up to 8 kHz if possible. Should there be an air conduction threshold of  $\geq 15$  dB, the subject should undergo bone conduction testing at that frequency if that threshold is for the frequency is 4 kHz or lower.
- High frequency audiometry (HFA) up to 16 kHz if possible.
- Tinnitus questionnaires (Tinnitus Handicap Inventory)
- Vestibular questionnaires (Dizziness Handicap)

For all tests, the same equipment should be used, as well as any repeat test to minimize technical variability.

More details can be found in Section 8.4.2. For description of these assessments refer to the Auditory and Vestibular Tests Manual.

All audiometric findings will be written on an auditory entry form and abnormal findings will be sent to the AVDSMB (consisting of a physician and audiologist) when required. The AVDSMB will decide if further dosing will occur, taking into account the stopping criteria.

### **7.3.7. Local Reaction of Injection Site**

The extent of local reaction on the injection site will be graded according to CTCAE 4.03, modified from the Food and Drug Administration (FDA) Guidance for Industry (FDA, 2007) and DAIDS criteria (Section 13.1).

Local reaction will be assessed at the timepoints specified in Section 7.1 and in Table 1.

### **7.3.8. Pregnancy Testing**

For female subjects of childbearing potential, a serum or urine pregnancy test (all women regardless of childbearing potential) will be performed at the timepoints specified in Section 7.1 and in Table 1.

A negative pregnancy result is required before the subject may receive the investigational product. Pregnancy tests will also be done whenever 1 menstrual cycle is missed during the active treatment period (or when potential pregnancy is otherwise suspected), and at the end of the study to confirm the subject has not become pregnant during the study. Pregnancy tests may also be repeated as per request of institutional review boards (IRBs)/Independent ethics committees (IECs) or if required by local regulations.

In the case of a positive confirmed pregnancy, the subject will be withdrawn from administration of investigational product.

If a study subject or study subject's partner becomes or is found to be pregnant during the subject's treatment with ELX-02, the Investigator must submit this information on a pregnancy report form to the CRO within 24 h of their knowledge of the event, preferably by fax or by e-mail. Contact information will be provided in a separate document.

If a participating subject's partner becomes pregnant during the study period, the Investigator will request her to sign an informed consent before following up her pregnancy course.

Follow-up is conducted to obtain general information on the pregnancy and its outcome. The Investigator will follow the pregnancy until completion (or until pregnancy termination) and notify the Sponsor of the outcome on a follow-up report.

If the outcome of the pregnancy meets the criteria for an SAE (i.e. ectopic pregnancy, spontaneous abortion, intrauterine fetal demise, neonatal death, or congenital anomaly [in a live-born baby, a terminated fetus, an intrauterine fetal demise, or a neonatal death]), the Investigator should follow the procedures for reporting SAEs.

More information can be found in Section 8.14.

### **7.3.9. Safety Blood and Urine, and Blood Sampling for Retention**

Safety laboratory evaluations and blood sampling for retention will be performed at the timepoints specified in Section 7.1 and in Table 1.

All blood samples for retention need to be taken after an overnight fast of at least 8h, except for the samples taken at 3h postdose on Day 1 and Day 29. Processing and storage of the samples are detailed in the laboratory manual provided by the Sponsor.

All blood samples for safety assessments should be taken after an overnight fast of at least 8h, except for the samples taken at 6h postdose on Day 1 and Day 29. At screening subjects will be instructed not to eat within 3h before arrival at the CPU.

The following safety laboratory assessment variables will be analyzed:

**Table 2: Safety Test**

Safety Blood Tests			
Hematology and Coagulation			
Red Blood Cell (RBC) count	Mean corpuscular hemoglobin (MCH)	White blood cells (WBC)	International normalized ratio (INR)
Hemoglobin	Mean corpuscular hemoglobin concentration (MCHC)	Platelets	WBC differential count
Hematocrit	Mean cell volume (MCV)	Prothrombin	
Biochemistry			
Total Protein	Aspartate aminotransferase (AST)	Alkaline Phosphatase (ALP)	Blood urea nitrogen
Albumin	Gamma glutamyl transferase (GGT)	Glucose	Serum Creatinine
Total Bilirubin	Lactate dehydrogenase (LDH)	Natrium (Sodium)	Glomerular filtration rate (GFR), (MDRD) (only at screening visit)
Alanine aminotransferase (ALT)	Creatine Phosphokinase	Potassium	
Hormones			
Serum $\beta$ -human chorionic gonadotropin (HCG) (screening only)	FSH (screening only)		
Serology (screening and follow-up only)			
HIV Ab	HBsAg	HCV Ab	
Urine Tests			
Urinalysis			
Proteins	Ketones	pH	Specific Gravity (SG)
Glucose	Urobilinogen	RBC	Bilirubin
Urine protein and Albumin (screening and EOS)			

Urine Biochemistry						
Creatinine						
Hormones						
Urine pregnancy test (all women, regardless of childbearing potential) Day -1, Day 7, Day 14, Day 21, Day 28, Day 36						
Drugs of Abuse (screening) Day -1, Day 7, Day 14, Day 21, and Day 28.						
Cannabinoids (THC)	Amphetamines	Benzodiazepines	Opiates			
Serum alcohol						

Abnormal safety tests may be confirmed by a single repeat, if deemed necessary.

The following microscopic parameters will be tested: RBC, WBC, bacteria, epithelial cells, granular casts, and hyaline casts.

After dosing, all lab tests outside the normal range will be repeated as clinically indicated until the values return to normal, or until the etiology has been determined and the condition considered stable. Abnormal laboratory test results that are considered to be clinically significant by the Investigator will be reported as an AE.

#### **7.3.9.1. Total Volume of Blood Sampling**

The total volume of blood that will be drawn from each subject will be approximately 542 mL for male and 547 mL for female subjects over a period of 12 weeks.

If necessary, in order to obtain additional information to ensure a subject's safety, additional blood samples (up to 50 mL) and/or urine samples may be taken at the discretion of the Investigator.

### **7.4. ELX-02 Pharmacokinetic Assessments**

#### **7.4.1. Blood Sampling**

Blood samples for determination of ELX-02 plasma concentrations will be taken using tubes containing K3EDTA at the timepoints specified in Section 7.1 and in Table 1.

Before blood draw, the sample will be identified with a coded label, bearing the following details:

- Study Number
- Subject Number
- Time Point

Sample handling, processing and shipment are described in the laboratory manual.

The actual sample collection date and exact clock time will be recorded. Sampling problems will be noted in the eSource.

Blood may be drawn either by direct venipuncture or through an indwelling IV cannula. If meals and blood collections coincide, blood will be collected before eating.

For any additional information related to laboratory related procedures, requirements and supplies, refer to the Laboratory Manual.

#### 7.4.2. Urine Collection

Urine samples, to measure the rate of ELX-02 excretion, will be collected at the timepoints specified in Section 7.1 and in Table 1.

- Day 1: Predose collection (first void in the morning). Urine samples for PK, biomarker, and creatinine analysis will be collected. Specific gravity will be calculated for the collection.
- Day 1 (0-12 hours postdose collection period): Subjects will be encouraged to void as frequently as possible (i.e., asked every hour if they can collect urine), and each individual sample will be collected separately. Each sample's weight will be recorded individually prior to removing urine for analyses. Specific gravity will be calculated for each collection.
- Day 1: 12-24 hours postdose collection period. This urine collection period includes all voids starting after 12h and includes the first void on the next day (i.e., 24h postdose void).  
The urine will be collected every 6h (i.e., 12-18h collection and 18-24h collection). The 12-18h voids and the 18-24h voids will be collected into separate urine collection containers.  
In addition, a single urine collection will be taken 24 hours after dosing using a third container (i.e., first morning void of Day 2). All urine containers will be weighed individually and the weights will be recorded. Urine samples for urinalysis, biomarker and creatinine analysis will be withdrawn from the single 24h urine void. Urine samples for PK analysis will be withdrawn from the pooled 12-18h and pooled 18-24h urine collection containers. Specific gravity will be calculated for each collection.
- Day 2 – Day 3: 24-48 hours postdose collection period. This urine collection period includes all voids subsequent to the 24h postdose void and includes the first void on the next day (i.e., 48 hours postdose void).  
The urine will be collected every 12h (i.e. 24-36h collection and 36-48h collection). The 24-36h voids and the 36-48h voids will be collected into separate urine collection containers.  
In addition, a single urine collection will be taken 36 hours after dosing using a third container and a single urine collection will be taken 48 hours after dosing using a fourth container (i.e. the first morning void of Day 3). All urine containers will be weighed individually and the weights will be recorded. Urine samples for urinalysis will be withdrawn from the single 48h urine void. Urine samples for biomarker and creatinine analysis will be withdrawn from the single 36h and 48h urine void. Urine samples for PK analysis will be withdrawn from the pooled 24-36h and pooled 36-48h urine collection containers. Specific gravity will be calculated for each collection.
- Day 3 – Day 4: 48-72 hours postdose collection period. This urine collection period includes all voids subsequent to the 48h postdose void and includes the first void on the next day (i.e., 72 hours postdose void).

During this collection period, subjects will be at home and collect the urine in urine jars (provided by the study site personnel). During this period, voids will be collected into a urine collection container. In addition, a single urine collection will be taken 72 hours after dosing using a second container. Urine samples for biomarker analysis and creatinine will be withdrawn from the single 72h urine void. Urine samples for PK analysis will be withdrawn from the pooled 48-72h urine collection container. Gravity will be calculated for each collection.

- Day 29: Predose collection (first void in the morning). Urine samples for PK, biomarker, and creatinine analysis will be collected. Specific gravity will be calculated for the collection.
- Day 29 (0-12 hours postdose collection period): Subjects will be encouraged to void as frequently as possible (i.e., asked every hour if they can collect urine), and each individual sample will be collected separately. Each sample's weight will be recorded individually prior to removing urine for analyses. Specific gravity will be calculated for each collection.
- Day 29: 12-24 hours postdose collection period. This urine collection period includes all voids starting after 12h and includes the first void on the next day (i.e., 24h postdose void).

The urine will be collected every 6h (i.e., 12-18h collection and 18-24h collection). The 12-18h voids and the 18-24h voids will be collected into separate urine collection containers.

In addition, a single urine collection will be taken 24 hours after dosing using a third container (i.e., first morning void of Day 30). All urine containers will be weighed individually and the weights will be recorded. Urine samples for urinalysis, biomarker and creatinine analysis will be withdrawn from the single 24h urine void. Urine samples for PK analysis will be withdrawn from the pooled 12-18h and pooled 18-24h urine collection containers. Specific gravity will be calculated for each collection.

- Day 30 – Day 31: 24-48 hours postdose collection period. This urine collection period includes all voids subsequent to the 24h postdose void and includes the first void on the next day (i.e., 48 hours postdose void).

The urine will be collected every 12h (i.e. 24-36h collection and 36-48h collection). The 24-36h voids and the 36-48h voids will be collected into separate urine collection containers.

In addition, a single urine collection will be taken 36 hours after dosing using a third container and a single urine collection will be taken 48 hours after dosing using a fourth container (i.e. the first morning void of Day 31). All urine containers will be weighed individually and the weights will be recorded. Urine samples for urinalysis will be withdrawn from the single 48h urine void. Urine samples for biomarker analysis and creatinine will be withdrawn from the single 36h and 48h urine void. Urine samples for PK analysis will be withdrawn from the pooled 24-36h and pooled 36-48h urine collection containers. Specific gravity will be calculated for each collection.

- Day 31 – Day 32: 48-72 hours postdose collection period. This urine collection period includes all voids subsequent to the 48h postdose void and includes the first void on the next day (i.e., 72 hours postdose void).

During this collection period, subjects will be at home and collect the urine in urine jars (provided by the study site personnel). During this period, voids will be collected into a urine collection container. In addition, a single urine collection will be taken 72 hours after dosing using a second container. Urine samples for biomarker analysis and creatinine will be withdrawn from the single 72h urine void. Urine samples for PK analysis will be withdrawn from the pooled 48-72h urine collection container. Specific gravity will be calculated for each collection.

After weighing and removing urine for analyses, the collection containers with remaining urine may be discarded.

**If urine cannot be obtained at a certain time interval it will be duly recorded and urine will be collected at the next time interval.**

Urine collection will be timed and measured for weight to determine the retained fraction of ELX-02 concentration and delay of excretion of the retained fraction and the PK.

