#### Day 3 (Discharge from CPU)

Before discharge (at approximately 48 hours after dosing), subjects will undergo the following assessments:

- Last urine collection added to the previous urine collection for PK.
- Urine samples for renal injury biomarkers, creatinine and general urinalysis (48h urine void).
- Assessment of local injection(s) reaction (48h).
- Vital signs (supine BP, HR, RR, and oral temperature) after 5 min in a supine position (48h)
- Weight.
- Physical examination (48h).
- 12-lead ECG (48h) taken after 5 minutes in a supine position
- Blood samples collection (48h):
  - Safety lab tests (48h)
  - PK (48h)
  - Blood sampling for housekeeping proteins (48h).
- AEs assessment and change in concomitant medication.
- Auditory and vestibular assessments (may be performed on Day 2, as well if not otherwise possible).

Subjects will be discharged following satisfactory clinical assessment by the Investigator. Two urine jars will be provided to the subject for 48-72h urine collection at home.

#### Day 4-Day 11-Day 18

Subjects will hand over the urine jars to the site personnel (only on Day 4), for the urine PK sampling from the collection 48-72h.

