4.3.1.4. Urine PK Parameters

The following urinary PK parameters will be calculated:

- Ae: Amount excreted in urine in an interval: 0-1h, 1-2h, 2-3h, 3-4h, 4-5h, 5-6h, 6-7h, 7-8h, 8-9h, 9-10h, 10-11h, 11-12h, 12-18h, 18-24h, 24-36h, 36-48h, 48-60h, and 60-72h on Day 1 and Day 29. Cumulative amount excreted will also be calculated, i.e. Ae_{12h}, Ae_{24h}, Ae_{48h}, Ae_{72h}.
- R_{max}: Maximum amount excreted in urine in a collection interval.
- t_{R_{max}}: Time when maximum amount is excreted in urine. This will be mid-point of the collection interval.
- Fe: Percent of dose excreted in urine on Day 1 and Day 29 (Ae_(t)/dose*100), where t = 12, 24, 48, 72 (will be shown as Fe_{12h}, Fe_{24h}, Fe_{48h}, Fe_{72h}).
- CL_R: Renal clearance on Day 1 and Day 29 (CL_R = Ae_{72h} / plasma AUC_{72h}). If Ae_{72h} or AUC_{72h} is not available, CL_R will be calculated based on data up to 48 hours.

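### Protocol 7.4.2, Protocol 7.1 and SAP 4.3.1.3 disagree on whether the 24h, 36h, 48h and 72h voids count in urine PK; followed literally, 7.4.2 biases late-interval Ae low

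*Protocol*

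**What the plan says.** Protocol 7.4.2 splits the urine after 12h into three periods, handled alike after the Day 1 and Day 29 doses.

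- **12-24h.** The definition takes in the 24h void: "This urine collection period includes all voids starting after 12h and includes the first void on the next day (i.e., 24h postdose void". That void is then diverted: "a single urine collection will be taken 24 hours after dosing using a third container (i.e., first morning void of Day 2". It is assigned to urinalysis, biomarkers and creatinine, while "Urine samples for PK analysis will be withdrawn from the pooled 12-18h and pooled 18-24h urine collection containers".
- **24-48h.** The period runs from after the 24h void through the 48h void. The 36h and 48h voids go into a third and a fourth container, and "Urine samples for PK analysis will be withdrawn from the pooled 24-36h and pooled 36-48h urine collection containers".
- **48-72h, at home.** The period includes the 72h void, which goes into a second container for biomarkers and creatinine. PK comes from the pooled container.

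Containers up to 48h are weighed individually. The section ends by letting leftover urine be thrown away and by giving the aim of timing and weighing: "to determine the retained fraction of ELX-02 concentration and delay of excretion of the retained fraction and the PK".

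Other current text points elsewhere. Protocol 7.1, for discharge on Day 3 and Day 31, has "Last urine collection added to the previous urine collection for PK", which at about 48h reads as the 48h void. It also provides two home jars and has the jars handed in for 48-72h PK sampling. SAP 4.3.1.3 pools urine in each interval, measures the volume and assays an aliquot, with no void excluded. SAP 4.3.1.4 then derives Ae per interval, cumulative Ae, "Percent of dose excreted in urine on Day 1 and Day 29" at 12, 24, 48 and 72h, and CL_R as Ae72h over AUC72h.

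**The concern.** Urine PK parameters are a primary endpoint (Protocol 2.2.1). Drug passed into a container that is never assayed cannot be told apart from drug still in the body, so Ae, Fe and CL_R would go down and the apparent retained fraction up. A first morning void holds everything formed since the last void of the night, so the container set aside at 24h may hold most of the 18-24h urine. The loss would also vary with each subject's voiding habits, which adds spread that is not pharmacokinetic.

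Section 7.4.2 names PK when a single void serves PK, as for the predose void. For the four later voids it does not.

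**Working it through.** The plan gives no figure to reproduce, so this is a mass balance of what would be lost if all four single voids went unassayed.

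**Inputs from the documents.** Terminal half-life h is 2 to 4 h (Protocol 1.2.2) or 2 to 8 h (SAP 1.1.1). Protocol 1.2.2 reports near-complete urinary recovery within 12h. The intervals are those in 7.4.2.

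**Assumptions.** Mono-exponential excretion, complete eventual urinary recovery, and the time since the previous void, which the documents do not give. Three cases for the 24h/36h/48h/72h voids: A, 2 h each; B, 6/3/6/6 h; C, the whole interval, 6/12/12/24 h.

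**Formula.** Share of dose excreted from a to b = 2^(-a/h) - 2^(-b/h). AUC is untouched, so CL_R falls by the same percentage as Ae72h.

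**Which half-life fits.** Recovery in 0-12h is 1 - 2^(-12/h): 98.4% at 2 h, 87.5% at 4 h, 64.6% at 8 h. The 8 h value does not fit near-complete recovery by 12h.

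**The 18-24h interval.** True content:
- h = 2: 2^-9 - 2^-12 = 0.1953% - 0.0244% = 0.171% of dose
- h = 4: 2^-4.5 - 2^-6 = 4.419% - 1.563% = 2.857% of dose

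Content of the 24h void in case A:
- h = 2: 2^-11 - 2^-12 = 0.0244%, or 14% of the interval
- h = 4: 2^-5.5 - 2^-6 = 0.647%, or 23% of the interval

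In cases B and C the void holds the whole interval and 100% is lost.

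**All four voids lost** (percent of dose; Fe72h is essentially 100%, so this is also the relative fall in Fe72h and CL_R):

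| h | Case | 24h void | 36h | 48h | 72h | Total |
|---|---|---|---|---|---|---|
| 2 h | A | 0.024 | 0.000 | 0.000 | 0.000 | 0.025 |
| 2 h | B | 0.171 | 0.001 | 0.000 | 0.000 | 0.172 |
| 2 h | C | 0.171 | 0.024 | 0.000 | 0.000 | 0.195 |
| 4 h | A | 0.647 | 0.081 | 0.010 | 0.000 | 0.738 |
| 4 h | B | 2.857 | 0.133 | 0.045 | 0.001 | 3.035 |
| 4 h | C | 2.857 | 1.367 | 0.171 | 0.024 | 4.419 |

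The fall is therefore about 0.03% to 4.4%. Returning the 48h void, as 7.1 directs, changes little: the largest total moves from 4.42% to 4.25%.

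**Longer overnight gap.** If the 24h void holds urine from 15h, at h = 4 it contains 2^-3.75 - 2^-6 = 7.43% - 1.56% = 5.9% of dose. With the case B values for the other voids the total is 6.0%. Allowing for SC absorption with tmax 0.5-1 h gives 6.0-6.2% for the 24h void.

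**Retained fraction at 72h.** The true value is 2^(-72/h), below 0.001% of dose at 2-4 h. The apparent value would be 0.03% to 4.4%.

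**Unaffected.** Ae over 0-12h and Fe12h; also Rmax, provided peak excretion falls within 0-12h.

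**The case against.** The strongest reply is that this is an inconsistency and not a demonstrated loss. SAP 4.3.1.3 pools all urine in an interval. Section 7.1 returns the 48h void and collects the home jars for PK. Every container up to 48h is weighed, and 7.4.2 says the weights serve the retained fraction. The protocol already lets one void serve both purposes, since the 12h biomarker sample comes from the last void of the 0-12h PK collection. The laboratory manual, which is not available here, may settle the matter. Most of this stands: a reader might infer that Ae, Fe72h and CL_R are certainly too low, and the documents do not show that. But none of these passages specifically returns the 24h or 36h void, and the 24h void carries about two thirds or more of the loss in every case above. The SAP rule also does not track the collection closely: 4.3.1.3 and 4.3.1.4 list intervals within 48-72h, while 7.4.2 collects a single 48-72h pool.

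A reader might also take the SAP's 8 h half-life and infer losses of 15% or more in Fe72h and CL_R (3.5% to 20.9% in cases A to C). That applies the slowest terminal value to the whole dose and implies only 64.6% recovery by 12h, against the protocol's own report. Protocol 1.1.2 describes multi-exponential decay, so a slow tail can coexist with high early recovery. In that case the total loss is small, although the tail is what the late voids measure.

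Two further points are fair. The 100% loss of Ae18-24h rests on an assumed voiding pattern, and subjects are encouraged to drink hourly up to 10h after dosing. The retained fraction is a stated aim in 7.4.2 but not a listed SAP parameter; it would be read from 100% minus Fe72h.

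**Conclusion.** The passages conflict and need reconciling. If 7.4.2 is followed literally, Ae from 18-24h onward is biased low: by 14% to 100% for Ae18-24h at a 2-4 h half-life, with the upper end requiring that the first morning void be the only one after 18h. The apparent retained fraction at 72h would be 0.03% to 4.4% of dose against a true value below 0.001%. Fe72h and CL_R move little, by about 0.03-4.4%, or about 6% if the 24h void reaches back to 15h. These are assumed cases, not bounds; they rest on mono-exponential excretion, complete urinary recovery and void timings that the documents do not give. Whether any urine was actually left out cannot be decided from the documents. The point concerns late-interval excretion, not overall recovery or early renal clearance.

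**What to change.** **Protocol 7.4.2, 7.1 and SAP 4.3.1.3.** Use one common sentence: after the urinalysis, biomarker and creatinine aliquots are taken, the remainder of each 24h, 36h, 48h and 72h void is returned to its interval pool before the PK aliquot is drawn, and the amount removed is recorded. The laboratory manual should match.

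**SAP 4.3.1.4.** SAP 1.2.1 already lists the final doses for all seven cohorts, so the protocol sentence may come too late for them. For cohorts where the voids were not pooled:

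- Where a pool sample and a spot-void weight both exist, give a sensitivity estimate: Ae = pool concentration x (pool volume + spot-void volume), converting weight to volume with the recorded specific gravity.
- Where the pool is empty or no weight exists, report Ae and Fe after 18h as lower bounds. The second situation may arise for 48-72h, whose bullets carry no weighing instruction of their own.
- Report CL_R over 0-12h as well, as Ae12h/AUC12h. Each void there is collected individually and none is set aside in an unsampled container. The SAP's 48h fallback for CL_R does not avoid the problem.

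**Cost.** One handling sentence, a short SAP paragraph and an added AUC12h, for which the 12h plasma sample is already planned. No extra visit or assay is needed. The weakness is that the add-back assumes equal concentration in the two containers, so it should stay a sensitivity estimate.
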